**Arm 1 of algorithm:**

- If blood pressure (BP) ≤ ULN, continue XL184 at the same dose.

**Arm 2 of algorithm:**

- If BP ≤ 10 mm Hg above the ULN, continue XL184 at the same dose and recheck the BP within 72 hours.
- If the BP is ≤ ULN on recheck, continue XL184 at the same dose.
- If the BP remains above the ULN on recheck, then start antihypertensive therapy and follow Arm 3 of the algorithm from the point that anti-hypertensive therapy is started.

**Arm 3 of algorithm:**

- If BP is 11 to 25 mm Hg above the ULN on  $\geq 2$  of 3 measurements or  $> 35$  mmHg above baseline on  $\geq 2$  of 3 measurements, start anti-hypertensive therapy, continue XL184 at the same dose, and monitor BP at least twice weekly.
  - If the BP returns to  $\leq$  ULN within 14 days, continue XL184 at the same dose and continue anti-hypertensive therapy.
  - If the BP remains elevated  $\leq 25$  mm Hg above the ULN or  $> 35$  mm Hg above baseline for more than 14 days after the institution of anti-hypertensive therapy, **hold** XL184, monitor BP at least every 3 days, and follow Arm 4 of the algorithm from the point that XL184 is held. The antihypertensive therapy should be continued until the BP is less than the ULN.
    - If the BP returns to  $\leq$  ULN within 14 days, restart XL184 at a reduced dose (see [Section 5.11](#)).
    - If the BP remains  $>$  ULN for more than 14 days, patient is Off Protocol Therapy.
  - If the BP increases to  $> 25$  mm Hg above the ULN despite anti-hypertensive therapy, **hold** XL184, but continue the anti-hypertensive agent(s). Monitor the BP as clinically indicated and follow Arm 4 of the algorithm from the point that XL184 is held.
    - If the BP is  $\leq$  ULN within 14 days, XL184 may be restarted at a reduced dose (see [Section 5.11](#)).
    - If the BP is  $>$  ULN for  $> 14$  days, the patient is Off Protocol Therapy.

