 If BP > 25 mm Hg above ULN for age (verified) or Grade 4 HTN at any time, hold drug. Study drug should also be held for BP ≤ 25 mm Hg above the ULN age for > 14 days or 35 mm Hg above baseline for > 14 days. Antihypertensive agents can be used to control hypertension as clinically indicated after study drug is held.

 Anti-hypertensive therapy should be prescribed as clinically indicated, including the use of multiple anti-hypertensive agents.

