**Arm 4 of algorithm:**

- If BP is  $> 25$  mm Hg above the ULN **hold** XL184, monitor BP and administer anti-hypertensive therapy as clinically indicated.
  - If the BP returns to  $\leq$  ULN within 14 days, XL184 may be restarted at a reduced dose (see [Section 5.11](#)).
  - If the BP is  $>$  ULN for  $>14$  days, the patient is Off Protocol Therapy.

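### Section 5.5 can tell a site both to keep and to hold XL184 when blood pressure is within the ULN but more than 35 mm Hg above a low baseline

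*Combined protocol and SAP*

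**What the plan says.** Section 5.5 sets the ULN at 140/90 mm Hg for adults and at the 95th percentile for age, height and gender for children (Appendix V). Baseline is the BP at the enrolment examination. Section 3.2.7.6 caps BP at entry but sets no lower limit.

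**Rules that use baseline**
- Arm 3 entry: BP 11 to 25 mm Hg above the ULN, or more than 35 above baseline, on at least 2 of 3 "measurements, start anti-hypertensive therapy, continue XL184 at the same dose, and monitor BP at least twice weekly".
- Arm 3 hold: BP remains elevated by up to 25 mm Hg above the ULN, or more than 35 "mm Hg above baseline for more than 14 days after the institution of anti-hypertensive therapy".
- Footnote 3 hold: among other triggers, "35 mm Hg above baseline for > 14 days". No greater-than sign is printed before the 35.

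**Rules that use the ULN only**
- Arm 1: BP at or below the ULN, same dose.
- Arm 3 keep-dose: BP returns to at or below the "ULN within 14 days, continue XL184 at the same dose and continue anti-hypertensive therapy".
- Arm 3 restart after a hold: BP returns to at or below the "ULN within 14 days, restart XL184 at a reduced dose".
- Arm 4 restart, to which the Arm 3 hold refers: BP returns to at or below the "ULN within 14 days, XL184 may be restarted at a reduced dose".
- Arm 3 off-therapy: BP remains above the "ULN for more than 14 days, patient is Off Protocol Therapy". Arm 4 has an equivalent test.

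Nothing in the written arms or footnotes says which rule prevails when BP is within the ULN but more than 35 mm Hg above baseline.

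**The concern.** The hold can be triggered on one reference (baseline), while the decisions to keep the dose or restart use another (the ULN). For a patient with a low baseline, the same readings can satisfy both the instruction to continue at the same dose and the instruction to hold. Two sites could then treat identical patients differently.

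The hold branch is not neutral. It leads to a restart at a reduced dose. Section 5.3.1 does not allow re-escalation, and section 5.3.3 allows two reductions (one if BSA is 0.35–0.39). The restart test also does not ask whether the rise that caused the hold has resolved.

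**Working it through.** The plan states no figure on this point, so the check is for logical overlap.

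**1. When both rules apply.** The keep-dose test needs BP ≤ ULN. The hold test needs BP > baseline + 35. Both can be true only if baseline + 35 < ULN, that is, baseline < ULN − 35.

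- Adults: 140 − 35 = 105 systolic; 90 − 35 = 55 diastolic.
- Children, Appendix V, 50th height percentile:

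| Group | ULN | Overlap if baseline is below |
|---|---|---|
| Boys ≥ 17 | 136/87 | 101/52 |
| Boys 12 | 123/81 | 88/46 |
| Boys 2 | 106/61 | 71/26 |
| Girls ≥ 17 | 129/84 | 94/49 |
| Girls 12 | 123/80 | 88/45 |
| Girls 2 | 105/63 | 70/28 |

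Baselines that low are unlikely in young children, so the overlap mainly concerns adults and older adolescents.

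**2. Width of the conflict band.** It runs from just above baseline + 35 up to the ULN. For adult systolic BP in whole mm Hg:
- baseline 100: 136–140
- baseline 95: 131–140
- baseline 90: 126–140

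**3. Worked case.** An adult with baseline systolic 100 and ULN 140 reaches 152, falls to 138 by day 14 of antihypertensive therapy and stays there.
- Entry: 152 − 140 = 12, within 11–25, so Arm 3 applies.
- Keep-dose: 138 ≤ 140 within 14 days, so the same dose continues.
- Hold: 138 − 100 = 38 > 35, and BP has been above 135 throughout. From day 15, XL184 is held.
- Restart, if held: 138 ≤ 140 is already met, so a reduced dose can follow with BP unchanged.

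**4. What the baseline limb adds.** BP up to 25 mm Hg above the ULN for more than 14 days is already held under the first limb. BP more than 25 above the ULN is held at once. The baseline limb therefore adds a hold only when BP ≤ ULN, which is where it meets the keep-dose test.

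**5. Size of the first reduction.** Comparing Appendix IV with section 5.11 over the 13 BSA bands, the smallest cut in weekly dose is 25% (for example 160 to 120 mg: 40/160) and the largest is 40% (100 to 60 mg: 40/100). For BSA ≥ 1.37 m² the cuts are:
- 420 to 300 mg: 28.6%
- 480 to 360 mg: 25%
- 560 to 420 mg: 25%
- 600 to 420 mg: 30%

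**The case against.** The strongest reply is that Arm 3 has two sibling branches: BP comes back within the ULN, or it *remains elevated*. Section 5.5 tends to use *elevated* for BP above the ULN, since repeat measurements continue until BP is within it. On that reading, the patient at 138 has taken the first branch and the hold never arises. This is plausible for the Arm 3 bullet. It makes the baseline limb redundant, however (step 4), and it does not dispose of footnote 3, which states the baseline hold without that word. Nor does it help to count a return to the ULN only from the hold: a patient held at 138 would then fit neither the restart nor the off-therapy test.

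The algorithm diagram that footnote 3 annotates could not be seen and may settle the order of the branches. That limit stands. There are also partial safeguards: section 5.2 asks that the Study Chair be told of any dosage modification (in the haematological section, though the wording is general), and section 5.5 strongly recommends nephrology or cardiology input. These may catch an ambiguous case but do not say which rule applies.

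A reader might infer more than the text supports:
- *That the off-therapy test can never apply.* It fails only while BP stays within the ULN.
- *That antihypertensives may be stopped.* The instruction "The antihypertensive therapy should be continued until the BP is less than the ULN" sets a minimum duration; it does not tell anyone to stop.
- *That Arms 1 and 3 disagree on dose at entry.* Both continue XL184 at the same dose; they differ only on starting antihypertensives.
- *That footnote 3 says more than 35.* It prints 35 alone. Read as 35 or more, its adult systolic boundary would be a baseline of 105 or lower.

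**Conclusion.** The conflict holds for the written arms and footnote 3. When BP is at or below the ULN but more than 35 mm Hg above baseline for more than 14 days on antihypertensives, the text supports either an unchanged dose or a hold. The hold can be followed directly by a 25–40% cut in weekly dose that cannot be reversed.

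Its reach is narrow. It needs a baseline more than 35 mm Hg below the ULN and BP sustained in a band of about 5 mm Hg at an adult systolic baseline of 100, or 15 at 90. The documents give no frequency for such patients.

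A reader might go on to infer harm to the response or disease control results. The documents do not support that: the group is small and unquantified, and the rule does not enter the sample size or error rates. The conclusion rests on the written text, with the diagram unseen. Priority: a minor correction to a safety rule.

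**What to change.** Preferred: delete the baseline limb from the Arm 3 hold bullet and from footnote 3. The hold would then match the hypertension thresholds for dose-limiting toxicity in section 5.1.1, which have no baseline term. Keep a rise of more than 35 mm Hg above baseline as the trigger to start antihypertensives and twice-weekly monitoring, and add a cross-reference in Arm 1 sending such patients to Arm 3. The downside is that a sustained rise within the ULN would no longer trigger a hold.

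Alternative, if the clinical team wants to keep the baseline hold: require BP to be no more than 35 mm Hg above baseline, as well as within the ULN, in the keep-dose test and in the Arm 3 and Arm 4 restart tests. Whether to add the same condition to the off-therapy test needs a separate decision, because it would remove patients whose BP is within the ULN.

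Adding a condition that BP also be above the ULN to the existing limb would not help, because it would leave the limb redundant.

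Under either option, check the algorithm diagram and make it match. The administrative cost is amended wording in section 5.5. No new measurement is needed, since baseline BP is already recorded.

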**Arm 4 of algorithm:**

- If BP is  $> 25$  mm Hg above the ULN **hold** XL184, monitor BP and administer anti-hypertensive therapy as clinically indicated.
  - If the BP returns to  $\leq$  ULN within 14 days, XL184 may be restarted at a reduced dose (see [Section 5.11](#)).
  - If the BP is  $>$  ULN for  $>14$  days, the patient is Off Protocol Therapy.

**Arm 5 of algorithm:**

- If the participant develops Grade 4 hypertension, **discontinue** XL184, monitor BP and administer anti-hypertensive therapy as clinically indicated. The patient is Off Protocol Therapy.

**Should initiation of anti-hypertensive therapy be required, single agent therapy (commonly including the calcium channel blockers amlodipine or nifedipine, which are permissible without discussion with the study chair) should be started and the blood pressure should be monitored at least twice weekly until BP is  $<$  ULN.**

### 5.6 Dose Modifications for Thromboembolic Events

Subjects who develop a pulmonary embolism (PE) or deep venous thrombosis (DVT) should have XL184 treatment held until therapeutic anticoagulation with heparins (eg, LMWH) is established. (Note: therapeutic anticoagulation with oral anticoagulants or oral platelet inhibitors such as clopidogrel is not allowed in this study). XL184 treatment may be resumed in subjects who are stable and have uncomplicated PE or DVT and are deriving clinical benefit from XL184 treatment (The drug may be resumed with a dose reduction if the DVT is dose-limiting (i.e.,  $\geq$  Grade 3) and if the patient is deriving clinical benefit.) During anticoagulation treatment, subjects need to be monitored on an ongoing basis for bleeding risk and signs of bleeding which may require additional or more frequent laboratory tests according to institutional guidelines. If there are any signs of clinically relevant bleedings, XL184 treatment should be interrupted immediately and the investigator/ sponsor contacted to discuss further study participation. Subjects with life-threatening PE or DVT should have study treatment discontinued unless toxicity can be managed and subject is deriving clear clinical benefit as determined by the investigator and agreed by the investigator/ sponsor.

Arterial thrombotic events (e.g., transient ischemic attack, myocardial infarction) have been observed in studies with XL184. Subjects should be evaluated for preexisting risk factors for arterial thrombotic events and cardiac or thromboembolic events that occurred before initiation of study treatment. XL184 treatment should be discontinued in subjects who develop an acute myocardial infarction, cerebral infarction or any other clinically relevant arterial thromboembolic complication.

### 5.7 Dose Modifications for Liver Toxicity

XL184 should be held for Grade 3 elevation of ALT, AST or bilirubin. Note: For the purposes of this trial the ULN for ALT is defined as 45 U/L regardless of the patient's baseline, and the ULN for AST is defined as 50 U/L. XL184 may be re-administered at the same dose if levels of ALT, AST and bilirubin meet eligibility criteria or baseline within 7 days of drug discontinuation. Elevated laboratory parameters should be checked at least twice weekly until eligibility criteria are met.

If lab values do not resolve to initial eligibility criteria or baseline within 7 days of interruption or if toxicity recurs with re-challenge, then this will be considered dose-limiting per [Section 5.1.1](#). The XL184 will be reduced according to [Section 5.11](#) when eligibility criteria are met.

### 5.8 Dose Modifications for Pancreatic Toxicity

XL184 should be held if patient experiences Grade 3 asymptomatic amylase or lipase elevation. Elevated laboratory parameters should be checked at least twice weekly until  $\leq$  Grade 1.

If lab values do not resolve to  $\leq$  1 Grade within 7 days of interruption or if toxicity recurs with re-challenge, then this will be considered dose-limiting per [Section 5.1.1](#). XL184 will then be dose-reduced according to [Section 5.11](#) when eligibility criteria are met.

### 5.9 Dose Modifications for Diarrhea

See [Appendix VI](#) for specific guidelines for supportive care measures for patients who develop therapy-associated diarrhea.

- If dose-limiting Grade 3 ( $>$  3 days) or Grade 4 therapy-associated diarrhea is experienced by a patient despite maximal use of anti-diarrheal medications, the dose of XL184 should be reduced per [Section 5.11](#).

## 5.10 Monitoring for Specific Toxicities

### 5.10.1 Growth Plate Toxicity

Patients  $\leq$  18 years of age at enrollment will have a plain AP radiograph of a single proximal tibial growth plate obtained prior to the first dose of protocol therapy.

- a. If patients are found to have a closed tibial growth plate, no further radiographs will be required.
- b. If patients are found to have an open tibial growth plate, then repeat plain AP radiographs of the same tibial growth plate will be obtained prior to Cycles 2, 5 and every 6 cycles thereafter until off protocol therapy.
  - Patients with evidence of growth plate thickening or other changes should have a knee MRI performed to further assess the degree of physal pathology and undergo more frequent x-ray follow up. MRI should be performed without contrast.
  - Patients with knee MRI changes should be managed in an individualized manner. Decisions regarding continuation of XL184 should be made after discussion with the Study Chair or Study Vice-Chair, taking into account the presence of any symptoms referable to the knee as well as the patient's response to XL184. Consultation with an orthopedic surgeon may also be indicated. Plans for follow-up imaging will also be made on an individualized basis, taking into account the presence of symptoms at the knee or other joints as well as the decision to continue XL184 or not.

### 5.10.2 Thyroid Toxicity

Patients found to have an abnormal TSH level should have a free T4 level measured. Thyroid toxicity will be handled like any other non-hematological toxicity. Guidance on the management of patients who develop hypothyroidism is included below.

Patients with Grade 2 hypothyroidism adequately managed with thyroid hormone replacement may continue on protocol therapy. Patients with Grade 3 or greater hypothyroidism will be considered to have had a dose-limiting toxicity. These patients should be managed according to [Section 5.3](#) and should also be evaluated by an endocrinologist for further management. Patients who enter the study on thyroid replacement should have their medication adjusted to maintain TSH in the normal range.

### 5.10.3 QT Prolongation

If the average QTcF from the three ECGs is  $>$  500 ms or increased by  $>$  60 ms above baseline.

The following actions must be taken:

- Withhold study treatment
- Hospitalize symptomatic subjects (e.g., with palpitations, dizziness, syncope, orthostatic hypotension, a significant ventricular arrhythmia on ECG) for a thorough cardiology evaluation and management.
- Consider cardiology consultation for asymptomatic subjects for evaluation and management.
- Check electrolytes, especially magnesium, potassium and calcium; correct abnormalities as clinically indicated.
- Check concomitant medications for any medication that may have contributed to QT prolongation, and if possible, discontinue these medications (See [Appendix VIII](#) for a list of drugs that prolong QTc).

- Repeat ECG triplicates hourly until the average QTcF is  $\leq 500$  msec, or otherwise determined by consultation with a cardiologist or appropriate expert.

Subjects with QTc prolongation and symptoms must be monitored closely until the QTc elevation and symptoms have resolved. Study treatment may be restarted at a reduced dose level if **all** of the following conditions are met:

- Symptoms are determined to be unrelated to the QT interval prolongation
- The QTcF value  $> 500$  ms or increase of  $> 60$  ms above baseline is not confirmed according to protocol procedures
- Study treatment has been interrupted through a minimum of 1 week following the return of the QTcF to  $\leq 500$  msec or return to  $\leq 60$  ms above baseline.
- QT prolongation can be unequivocally associated with an event other than XL184 administration and is treatable/has been resolved
- Sponsor has reviewed all available information and has agreed to the continuation of study treatment.

Following re-initiation of study treatment, ECGs must be repeated weekly for 2 weeks, then every 2 weeks for 1 month, then according to the protocol-defined time points.

All study treatment must be permanently discontinued if either of the following applies:

- Cardiac evaluation confirms that symptoms are the consequence of QT interval prolongation
- Recurrence of QTcF prolongation (confirmed by central ECG lab) after re-initiation of study treatment at a reduced dose

5.11 **XL184 Dose Reduction Table**

XL184 (Cabozantinib) 40 mg/m^2/day		
BSA (m^2)	Weekly Dose/Schedule for 1st Dose Reduction due to Toxicity	Weekly Dose/Schedule for 2nd Dose Reduction due to Toxicity
0.35 – 0.39	60 mg = 20 mg M, W, F (or Day 1, 3, 5 of each week)	Off therapy
0.40 – 0.45	80 mg = 20 mg M, W, F, Sun (or Day 1, 3, 5, 7 of each week)	60 mg = 20 mg M, W, F (or Day 1, 3, 5 of each week)
0.46 – 0.55	100 mg = 20 mg M, W, Th, Sat, Sun (or Day 1, 3, 4, 6, 7 of each week)	60 mg = 20 mg M, W, F (or Day 1, 3, 5 of each week)
0.56 – 0.64	120 mg = 20 mg M, T, W, F, Sat, Sun (or Day 1, 2, 3, 5, 6, 7 of each week)	80 mg = 20 mg M, W, F, Sun (or Day 1, 3, 5, 7 of each week)
0.65 – 0.78	140 mg = 20 mg Daily	100 mg = 20 mg M, W, Th, Sat, Sun (or Day 1, 3, 4, 6, 7 of each week)
0.79 – 0.90	160 mg = 40 mg M, W, F, Sun (or Day 1, 3, 5, 7 of each week)	120 mg = 20 mg M, T, W, F, Sat, Sun (or Day 1, 2, 3, 5, 6, 7 of each week)
0.91 – 1.09	200 mg = 40 mg M, W, Th, Sat, Sun (or Day 1, 3, 4, 6, 7 of each week)	140 mg = 20 mg Daily
1.10 – 1.17	200 mg = 40 mg M, W, Th, Sat, Sun (or Day 1, 3, 4, 6, 7 of each week)	140 mg = 20 mg Daily
1.18 – 1.36	240 mg = 40 mg M, T, W, F, Sat, Sun (or Day 1, 2, 3, 5, 6, 7 of each week)	160 mg = 40 mg M, W, F, Sun (or Day 1, 3, 5, 7 of each week)
1.37 – 1.65	300 mg = 60 mg M, W, Th, Sat, Sun (or Day 1, 3, 4, 6, 7 of each week)	200 mg = 40 mg M, W, Th, Sat, Sun (or Day 1, 3, 4, 6, 7 of each week)
1.66 – 1.85	360 mg = 60 mg M, T, W, F, Sat, Sun (or Day 1, 2, 3, 5, 6, 7 of each week)	240 mg = 40 mg M, T, W, F, Sat, Sun (or Day 1, 2, 3, 5, 6, 7 of each week)
1.86 – 2.07	420 mg = 60 mg Daily	300 mg = 60 mg M, W, Th, Sat, Sun (or Day 1, 3, 4, 6, 7 of each week)
≥ 2.08	420 mg = 60 mg Daily	300 mg = 60 mg M, W, Th, Sat, Sun (or Day 1, 3, 4, 6, 7 of each week)

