### 5.1 Definition of Dose-Limiting Toxicity (DLT)

DLT will be defined as any of the following events that are at least (possibly, probably or definitely) attributable to XL184.

Dose limiting hematological and non-hematological toxicities are defined differently.

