#### 5.1.1 Non-Hematological Dose-Limiting Toxicity

- Any Grade 4 non-hematological toxicity
- Any Grade 3 non-hematological toxicity with the specific exception of:
  - Grade 3 nausea and vomiting of less < 3 days duration
  - Grade 3 diarrhea  $\leq$  3 days duration
  - Grade 3 liver enzyme elevation including ALT/AST/GGT/bilirubin that return to levels that meet initial eligibility criteria within 7 days of study drug interruption and that do not recur upon re-challenge with study drug. Note: For the purposes of this trial the ULN for ALT is defined as 45 U/L and the ULN for AST is defined as 50 U/L. See [Section 5.7](#) for dose modifications for liver toxicity. Adverse event grades will be based on increases above the upper limit of normal, regardless of the subject's baseline. See appendix XI for toxicity-specific grading table.
  - Grade 3 fever or infection < 5 days duration.
  - Grade 3 hypophosphatemia, hypokalemia, hypocalcemia and/or hypomagnesemia responsive to supplementation
  - Grade 3 asymptomatic amylase or lipase elevation that resolves to Grade 1 within 7 days of study drug interruption and that does not recur upon re-challenge with XL184. See [Section 5.8](#) for dose modifications for pancreatic toxicity.
  - Grade 3 proteinuria (urine protein/creatinine (P/C) ratio > 1.9) unless it is confirmed with a second measurement within 72 hours
- Any Grade 2 non-hematological toxicity that persists for  $\geq$  7 days and is considered sufficiently medically significant or sufficiently intolerable by patients that it requires treatment interruption
- Dose-limiting hypertension
  - Any Grade 4 hypertension
  - A blood pressure > 25 mmHg above the ULN confirmed by repeated measurement on the same day is dose limiting. For pediatric patients ULN is the 95th percentile for age, height, and gender ([Appendix V](#)) and for patients  $\geq$  18 years of age ULN is 140/90 mmHg.
  - In patients who begin antihypertensive therapy a blood pressure > 10 mmHg but  $\leq$  25 mmHg above the ULN ([Appendix V](#)) for > 14 days is dose limiting.
- QTc prolongation > 500 ms that persists despite correction of serum electrolyte abnormalities will be considered dose limiting

- Grade 2 or higher allergic reactions that necessitate discontinuation of study drug will not be considered a dose-limiting toxicity.

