### 5.3 **Dose Modifications for Non-Hematological Toxicity**

- 5.3.1 XL184 will be discontinued in cases of serious toxicities such as GI perforation, fistula formation, significant bleeding, significant thrombotic events (such as myocardial infarction, cerebral infarction, other serious arterial thromboembolic events), Grade 4 hypertension, reversible posterior leukoencephalopathy syndrome, or osteonecrosis of the jaw. For other toxicities, if a patient experiences non-hematological dose-limiting toxicity as defined in [Section 5.1.1](#), the treatment will be held. When the toxicity resolves to meet eligibility parameters or baseline within 21 days of drug discontinuation, the patient may resume treatment at the next lower dose level (see [Section 5.11](#)). Doses reduced for toxicity will not be re-escalated, even if there is minimal or no toxicity with the reduced dose.

5.3.2 If toxicity does not resolve to meet eligibility or baseline parameters within 21 days of drug discontinuation, the patient must be removed from protocol therapy. The exception to this is Grade 3 weight loss as it is unlikely that the patient would return to baseline within 21 days. Patients who experience Grade 3 weight loss may resume study medication after 21 days with a dose-reduction (see [Section 5.11](#)) if the patient is deriving benefit from therapy, the weight loss has stabilized and the treating physician feels it is in the best interest of the patient. Patients should be removed from protocol therapy if their weight loss is  $\geq 20\%$  from baseline and persists for  $\geq 28$  days after the introduction of supplemental NG/G tube feeding or TPN.

5.3.3 Two dose reductions will be allowed for toxicity. If a patient experiences a dose limiting toxicity after two dose reductions, the patient must be removed from protocol therapy. For patients with BSA 0.35-0.39, only 1 dose reduction will be allowed as the lowest weekly administered dose is 60 mg/week.

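### Section 5.10.3 bars restart after a confirmed QTc excess with a reversible non-XL184 cause, ties the recurrence stop to a central ECG laboratory the protocol does not set up, and leaves its scope against Section 5.3.1 unstated (minor)

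*Combined protocol and SAP*

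**What the plan says.** **Definition.** Section 5.1 states that "DLT will be defined as any of the following events that are at least (possibly, probably or definitely) attributable to XL184". Section 5.1.1 adds that "QTc prolongation > 500 ms that persists despite correction of serum electrolyte abnormalities will be considered dose limiting".

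**General rule.** Section 5.3.1 gives an open-ended list of serious toxicities that end treatment; QTc prolongation is not named. It continues "For other toxicities, if a patient experiences non-hematological dose-limiting toxicity as defined in" Section 5.1.1, and tells sites to hold the drug. Then: "When the toxicity resolves to meet eligibility parameters or baseline within 21 days of drug discontinuation, the patient may resume treatment". The resumed dose is one level down. Section 4.1.1 separately requires recovery to the eligibility criteria within 21 days for any dose reduction under Section 5.0. For QTc the eligibility limit is 480 ms (Section 3.2.7.4).

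**QT rule.** Section 5.10.3 requires a hold when the mean QTcF of three ECGs exceeds 500 ms or rises more than 60 ms above baseline. Restart at a reduced dose needs all of the following:
- any symptoms are judged unrelated to the prolongation;
- the value above 500 ms or the rise of more than 60 "ms above baseline is not confirmed according to protocol procedures";
- the drug has stayed off for at least one week after QTcF fell back to 500 ms or less, or to within 60 ms of baseline;
- "QT prolongation can be unequivocally associated with an event other than XL184 administration and is treatable/has been resolved";
- agreement from the sponsor after its own review of the case.

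Permanent discontinuation follows if symptoms are shown to result from the prolongation, or if QTcF prolongation recurs after restart and a central ECG laboratory confirms it.

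**The concern.** A re-exposure rule for a cardiac toxicity should give one answer for each type of event. This one does not, in three ways.

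1. The restart list joins a condition that fits a false alarm (the excess was not confirmed) to conditions that fit a real event (it returned to range, had another cause, and is treatable or resolved). Patients with a real, explained and reversed event are shut out.
2. The mandatory stop on recurrence rests on a reader whom the protocol does not provide.
3. For a recovered event possibly due to XL184, a site reading 5.3.1 alone may resume treatment, while a site reading 5.10.3 as covering every subject may not.

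At stake are consistent handling of a safety event across sites and, for some patients, avoidable loss of treatment.

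**Working it through.** No sample size, error rate or power is involved, so the check sets the rules side by side.

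**Step 1: the 5.10.3 restart list, case by case.** Assume in each case that any symptoms are unrelated, QTcF has been back in range for at least one week, and the sponsor agrees.

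| Event | Excess unconfirmed? | Cause unequivocally not XL184? | Restart under 5.10.3 |
|---|---|---|---|
| A. First reading high, not reproduced, other cause evident | yes | yes | allowed |
| B. Confirmed, resolved, clear reversible non-XL184 cause | no | yes | barred |
| C. Confirmed, resolved, possibly due to XL184 | no | no | barred |

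Case A shows that the list can be met. Case B is the defect. It is realistic: Section 4.1.4.5 allows QT-prolonging drugs with monitoring when they have to be used, and 5.10.3 tells sites to look for such drugs and stop them if possible. A site that does so successfully still cannot restart XL184. With no QT-related symptoms and no recurrence, Case B also meets neither permanent-stop criterion, so the section gives it no exit in either direction.

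**Step 2: the recurrence stop.** The central ECG laboratory appears only in this criterion. The ECG entries in Sections 4.2.2, 4.3.2 and 4.4.2 ask for an ECG with QTc interval and mention no central reading or transmission. Section 7.3 sets up central review of tumor imaging only. The table of contents lists no ECG-reading section. After a recurrence, three things remain usable: the 5.10.3 hold applies again at the same thresholds, any further restart again needs sponsor agreement, and Section 8.1 allows removal in the patient's best interest.

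**Step 3: Case C under the two sections.** Take a QTc above 500 ms that persists after electrolyte correction, is possibly due to XL184, and falls to 480 ms or less within 21 days.
- Sections 5.1 and 5.1.1: it is a dose-limiting toxicity.
- Section 5.3.1 alone: treatment may resume at the next lower dose, with no test of cause and no sponsor review.
- Section 5.10.3: an event at least possibly due to XL184 cannot be unequivocally due to something else, so the cause condition fails and restart is barred.

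The divergence is confined to events meeting the 5.1.1 definition. An excess that does not persist after electrolyte correction is not dose limiting on that line and falls to 5.10.3. The divergence also presumes that the 5.10.3 list reaches asymptomatic subjects, which the text leaves open: the list follows a sentence about subjects with symptoms, and its first condition concerns symptoms.

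**The case against.** The best defense is that Section 5 works specific-over-general throughout. Section 5.3.1 gives a permission, and toxicity sections narrow or change it without a precedence sentence. Hypertension is off therapy after 14 days without recovery (5.5), against 21 in 5.3.1; proteinuria resumes at a protein/creatinine ratio of 1.9 or less (5.4) rather than at the eligibility urine-protein level. Section 6.1 sends readers to the protocol for QTcF criteria, and 5.10.3 is the only supplied section that states any. A site following 5.10.3 breaches nothing in 5.3.1. Section 5.10.2 may refer to 5.3 simply because it has no restart rule of its own. This stands: the natural reading is that 5.10.3 governs. What it leaves open is whether asymptomatic subjects are included.

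Stronger readings that a reader might infer, and why they fail:
- *The two sections are flatly incompatible.* The drafting pattern just described resolves most of the tension.
- *The restart list is logically impossible.* Case A can pass. The list errs toward keeping patients off drug.
- *A patient with a recurrence stays on drug for want of a central reader.* The hold, the sponsor review and Section 8.1 prevent this.
- *The 500 ms return level in 5.10.3 undercuts the 480 ms eligibility level.* Section 4.1.1 applies to any reduced-dose restart, so the limits stack: the 500 ms or 60 ms level starts the one-week clock, and 480 ms must still be met.

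**Conclusion.** The point holds, at minor severity. The restart list shuts out confirmed, reversible events not caused by XL184, and the recurrence stop cannot be triggered as written. The relation of 5.10.3 to 5.3.1 is a matter of unstated scope rather than a contradiction.

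The number of patients affected cannot be computed, because the documents give no QTc event rate. It is probably small: the phase 1 list of Cycle 1 dose-limiting toxicities (41 enrolled, Section 2.4.1) does not include QTc prolongation, and Section 6.1 places it among events with insufficient evidence of causation, although Section 4.1.4.5 states an association. The primary endpoint and sample size are not affected.

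The conclusion assumes that an excess is confirmed by repeat triplicate ECGs, the only repeat procedure 5.10.3 describes, and that no central ECG reading is arranged in the contact and appendix pages absent from the review copy.

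**What to change.** - **Section 5.3.1:** state that 5.10.3 governs QTc events in symptomatic and asymptomatic subjects, with the 4.1.1 requirement (QTc of 480 ms or less within 21 days) still applying.
- **Section 5.10.3, restart:** replace the joint condition with two alternatives: (a) the excess is not confirmed on repeat triplicate ECGs; or (b) it is confirmed, has resolved, and has an identified cause other than XL184, to the standard of certainty the section already sets. Keep the symptom condition, the one-week interruption and sponsor agreement for both.
- **Section 5.10.3, recurrence:** replace central-laboratory confirmation with confirmation on repeat site triplicate ECGs, which the section already uses.

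The cost is amendment wording and a few event-driven ECGs. Two changes in practice follow. Confirmed, explained and resolved events could restart with sponsor agreement. Some XL184-attributable events that 5.3.1 alone would let resume could not; the clinical team should confirm that this is intended.
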